PRO assessments at treatment discontinuation and 4 weeks post-treatment discontinuation for all participants regardless of the reason for treatment discontinuation (toxicity, progression) will provide valuable information on HRQL and symptom burden. As noted by Rini et al. HRQL can appear to improve overall as the trial progresses due to participant selection bias. Participants with poorer performance status, more aggressive disease, and greater treatment toxicities come off treatment earlier. We may observe a high rate of attrition due to progression of illness. Patients on EE are expected to remain on treatment longer than patients on EP due to anticipated benefit in PFS. To obtain an unbiased assessment of HRQL and treatment toxicities, PRO assessment at the end of treatment and a short period of time following end of treatment (4 weeks) for all participants is needed. Otherwise, PRO assessments only capture data on participants who remain on treatment and are likely to be healthier, therefore, presenting a biased source of data that will likely indicate that HRQL improves over time. In addition, the assessment 4 weeks post-end of treatment will evaluate whether entinostat-related symptoms resolve within 4 weeks. This design (retaining participants who discontinue treatment) has been employed with other PROs studies such as the side effect sub-study of MA.27.

Rev. Add7

A PRO measure of breast cancer-specific symptoms will be administered at baseline, and every 28-day cycle for the first six months after randomization, and then every two cycles between 6 months and 1 year. After 1 year, the FBSI will be administered on the same schedule as tumor assessments until disease progression. The FBSI will be administered more frequently to allow for an assessment of time to treatment deterioration (TTD), a critical secondary endpoint.

The PRO measure of adherence to therapy, the Medication Adherence Scale - , will be administered as outlined in Section [5.6.3](#) (before Cycle 4, 7, 13, and end of protocol therapy). With the exception of baseline, these assessment time points correspond with other study PRO.

The FBSI and Medication Adherence Scale include 8 and 8 items each and the anticipated time to complete the 16 items is roughly 5-6 minutes. Please note there will be one Medication Adherence Scale form completed for each agent (entinostat/placebo and exemestane).

Rev. Add7

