#### 9.6.1 Statistical consideration for PROs

The primary objective of the PROs study is to test whether the overall HRQL is significantly worse in the Exemestane + Entinostat arm (arm A) compared to the Exemestane + Placebo arm (arm B) at month 3. The null hypothesis is that patients on the two arms have same overall HRQL. The alternative hypothesis is that patients on arm A have worse HRQL than patients on arm B. The endpoint for the objective is the overall HRQL score measured by the Trial Outcome Index (TOI), an aggregate score of the 5 items from the FACT-G-Physical subscale (GP2, GP3, GP4, GP6, and GP7), and 6 items from the FACT-G-Functional subscale (GF1, GF2, GF3, GF4, GF6, and GF7). Higher score represents better HRQL (score range 0-44).

Assuming an overall attrition rate of approximately 10% by month 3 for the PROs assessment in both arms, it is expected that about 324 refractory patients will be included for the primary analysis for HRQL. At month 3, a difference of 5 points in the overall HRQL score between the treatment arms would be considered clinically meaningful. The common standard deviation is expected to be 12 points. With 162 analyzable patients on each arm for the month 3 assessment, there will be about 93% power to test the difference using a two independent samples t test, assuming a two-sided type I error of 0.025.

The second objective of the PROs study is to assess differences between the two arms in symptoms associated with entinostat at month 3 (i.e., fatigue, nausea, anorexia and diarrhea, measured by PROMIS Fatigue short form, FAACT-additional concerns and FACIT-Diarrhea, respectively). The null hypothesis is that there is no difference between two arms regarding fatigue, nausea, anorexia and diarrhea at 3-month assessment. The alternative hypothesis is that patients on the Exemestane + Entinostat arm have more severe symptoms than patients on the Exemestane + Placebo arm. For each of the four symptoms, with 162 analyzable patients on each arm in the study, there will be an adequate power (80%) to detect an effect size of 0.40 and an excellent power (90%) to detect an effect size of 0.45, using two independent samples t test, assuming a two-sided type I error of 0.00625 (=0.025/4). The effect size is the difference in the survey score between two arms divided by the population standard deviation for each symptom.

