#### 9.6.2 Analysis plan for PROs

The analysis time for PROs endpoints is at about 40 months (24 months of accrual + 12 months of treatment + 1 month follow up after treatment + 3 months of data collection and cleaning) after study activation. Subscale scores for all endpoints will be prorated by multiplying the sum of the subscale by the number of items in the subscale, then dividing by the number of items actually answered: Prorated subscale score = (sum of items cores) \* (number of items in subscale) / (number of items answered). When there are missing data, prorating by subscale in this way is acceptable as long as more than 50% of the items are answered in each subscale. For overall QOL, the FACT-G scale is considered to be an acceptable indicator of patient quality of life as long as overall item response rate is greater than 80%. For the four symptoms, the measurement scales (i.e., PROMIS-Fatigue, FAACT-Additional Concerns subscale, FACIT-Diarrhea) must be completed over 50% of the items (e.g., 4 of 7 items, 6 of 11 items and 7 of 12 items) in order to consider each subscale score valid.

Standard descriptive and graphical analyses will be used initially to examine missing data patterns, and to understand the relationship between variables. The assessment scores for the four symptoms and HRQL will be compared between the two treatment arms at baseline, month 3, month 6, month 12, at the end of protocol treatment and 4-week post-treatment (regardless of the reasons for off treatment), using two independent samples t test (or Wilcoxon rank sum test if the distribution of the score is not symmetric). Change in the four symptoms and HRQL between month 3 visit and the baseline visit will be compared between the two arms using two independent sample t tests. Similar analyses will be conducted for each FACT-G subscales as well. The mean score and proportion of moderate/severe symptoms will be compared between treatment arms for each individual FACT-G item at month 3 using Wilcoxon rank sum test and Fisher exact test, respectively, as an exploratory analysis.

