Mixed effect models will be constructed as another exploratory analysis to estimate the time profile of HRQL in the two treatment arms and to evaluate treatment-by-time interactions. Time will be included as a continuous variable if there is a linear trend in HRQL over time or a set of dummy variables if non-linear trend exists for HRQL. Likelihood ratio test will be used for model selection. Adjusted covariates included in the mixed effect models will include patient demographic and disease characteristics, such as age, ECOG PS, disease stage, prior therapy, et al.

As an exploratory analysis, patient-reported outcomes will be correlated with PFS (prognostic value of PROs) in the study patients. Patients will be dichotomized (e.g., by median) and/or categorized into groups (e.g, quantiles) based on their HRQL at baseline and 3-month assessment. Kaplan-Meier method, log rank test and Cox models will be used to compare PFS between patients with good QOL and those with poor QOL in the overall patient population. The predictive value of QOL for benefit from entinostat therapy will be examined via the QOL-by-treatment interaction test in a Cox model for PFS. Landmark method will be used when we correlate QOL at month 3 with PFS, and PFS will be defined as time from landmark time point to disease progression or death for these analyses.

In all analyses, P-values will be two-sided. A level of 2.5% will be considered statistically significant for QOL comparison between two arms. For the four symptoms, a level of 0.625% will be considered statistically significant for comparison between treatment arms. For all other analysis, a level of 5% will be considered statistically significant. No adjustment will be made for multiple comparisons for individual FACT-G items.

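### Section 5.6 says the 4-week post-treatment form will show whether entinostat-related symptoms resolve, but Section 9.6.2 contains no analysis that answers that question

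*Combined protocol and SAP*

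**What the plan says.** Section 5.6.3 schedules PROMIS Fatigue, FAACT and FACIT-D at baseline, at the end of cycles 3, 6 and 12, at the end of protocol treatment, and 4 weeks later. The narrative that follows gives two reasons for the off-treatment forms. The main one is to avoid the selection bias that arises when only patients still on treatment are assessed. The second is that "the assessment 4 weeks post-end of treatment will evaluate whether entinostat-related symptoms resolve within 4 weeks".

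Section 9.6.2 compares scores between arms visit by visit, including "at the end of protocol treatment and 4-week post-treatment (regardless of the reasons for off treatment), using two independent samples t test", with a Wilcoxon test where scores are not symmetric. It plans one change score: "Change in the four symptoms and HRQL between month 3 visit and the baseline visit will be compared between the two arms". The longitudinal analysis is exploratory and is named for HRQL, not for the four symptoms: "Mixed effect models will be constructed as another exploratory analysis to estimate the time profile of HRQL in the two treatment arms". On significance levels it says: "For the four symptoms, a level of 0.625% will be considered statistically significant for comparison between treatment arms". A 5% level then covers every other analysis.

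Section 9.6.1 gives the month-3 power: "with 162 analyzable patients on each arm in the study, there will be an adequate power (80%) to detect an effect size of 0.40". It also states the MIDs: 3.0-5.0 points (0.4 to 0.63 SD) for fatigue, 6 points (0.53 SD) for FAACT, and 4 points (proposed as comparable to 0.5 SD) for FACIT-D.

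**The concern.** Whether symptoms resolve after stopping is a question about change: does a patient's score recover between the last on-treatment form and the form 4 weeks later, by more than placebo patients' scores move? A between-arm comparison at the later visit does not measure that recovery. Without a margin or an interval criterion it also cannot show that the remaining excess is small. Significance at end of treatment followed by non-significance at 4 weeks is not a test of change either.

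Section 1.5 says the PRO data are meant to inform counselling on risks and benefits. If a reader of the results took a null test at 4 weeks as evidence that symptoms clear, the error would favour entinostat. The paired forms that bear on the question are already collected for all three scales.

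**Working it through.** **1. The plan's own power figure.** Inputs from Section 9.6.1: 162 per arm (360 × 0.9 = 324, halved), two-sided level 0.025/4 = 0.00625, two-sample t test. The noncentral t gives 80.1% power at 0.40 SD and 90.2% at 0.45 SD, which reproduces the stated 80% and 90%.

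**2. Miss rate at the 4-week visit.** Miss rate = 1 − power. The documents give no number of forms for this visit. The range 103-137 per arm is an assumption: 60-80% of the 171 treated patients per arm that Sections 9.3.2 and 9.3.3 expect (0.6 × 171 ≈ 103; 0.8 × 171 ≈ 137).

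| Per arm | 0.40 SD, level 0.00625 | 0.40 SD, level 0.05 | 0.50 SD, level 0.00625 | 0.63 SD, level 0.00625 |
|---|---|---|---|---|
| 162 (month-3 figure) | 19.9% | 5.2% | 4.1% | 0.2% |
| 137 (assumed) | 29.0% | 9.0% | 8.5% | 0.7% |
| 103 (assumed) | 45.6% | 18.5% | 20.6% | 4.0% |

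The 5% column is needed because 0.00625 is derived for month 3. Section 9.6.2 applies 0.625% to the symptoms without naming a visit and then gives 5% for all other analyses, so either level could be read as applying at 4 weeks.

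**3. Is fewer than 162 plausible?** Section 9.6.2 times the PRO analysis at 24 months of accrual plus 12 of treatment and 1 of follow-up, plus cleaning. A patient still on treatment then has no post-treatment form. As an illustration only, take treatment duration as exponential with the planned PFS medians (7.1 and 4.1 months), accrual uniform over 24 months, and 12 to 36 months available for treatment to end. With λ = ln 2 / median, the fraction still on treatment is (e^(−12λ) − e^(−36λ)) / (24λ), which is 12.0% in arm A and 3.2% in arm B. Then 171 × 0.880 × 0.9 ≈ 135 and 171 × 0.968 × 0.9 ≈ 149 forms, applying the month-3 attrition of 10% to this visit. The miss rate at 0.40 SD and level 0.00625 is about 27%.

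**4. Which change analysis.** Suppose the end-of-treatment excess is 0.4 SD and the within-patient correlation is 0.6 (assumed). A comparison at 4 weeks adjusted for the end-of-treatment score estimates (4-week difference) − 0.6 × 0.4.
- Excess persists unchanged: adjusted 0.40 − 0.24 = +0.16 SD; plain change difference 0.40 − 0.40 = 0.
- Excess fully resolves: adjusted 0 − 0.24 = −0.24 SD; plain change difference 0 − 0.40 = −0.40 SD.

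A simulation gives the same values. The end-of-treatment score is itself affected by treatment, so adjusting for it distorts the contrast. The plain change difference does not have this problem.

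**5. Can an interval criterion be met?** The 95% half-width for the 4-week difference is 1.96 × √(2/n): 0.218 SD at 162, 0.237 at 137 and 0.273 at 103 per arm. If the true difference is zero, the chance that the upper bound falls below 0.4 SD is Φ(0.4/√(2/n) − 1.96): 95%, 91% and 82%. The criterion is achievable with the data scheduled.

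**The case against.** The strongest defence is that the plan nowhere says a non-significant 4-week test will be read as resolution. That is correct. A reader might infer such a rule because the between-arm test is the only inferential symptom result at that visit, but the documents state no rule in either direction. Descriptive and graphical analyses and an end-of-treatment arm comparison are also planned, so the size of the difference at each visit could be seen.

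Resolution is also a side rationale. It is not among the objectives in Section 2.2, is not one of the two PRO objectives in Section 9.6, and is not powered. Month 3 is the primary PRO comparison. This limits the importance of the point but does not supply the missing analysis.

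A reader might also take a 30-45% miss rate as a property of the plan. The documents do not support that. It requires roughly 135 down to 104 returned forms per arm, and the only stated number, 162, gives about 20%. Section 5.6.3 warns that attrition may be high without quantifying it, while Section 5.6.4 sets up mail and telephone collection to limit the loss. The 0.4 SD effect is the least favourable value in the fatigue MID range, and the significance level at this visit is ambiguous.

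Finally, recovery after stopping is hard to attribute. Patients who stop for progression may have disease symptoms changing at the same time. That stands, and it needs a caveat in any analysis.

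**Conclusion.** The gap is real but limited: Section 5.6 gives the 4-week form a purpose for which Section 9.6.2 has no matching analysis, definition or criterion. Absence of significance at that visit would not support a statement that symptoms resolve.

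The size depends on inputs the documents leave open. For a 0.4 SD excess the miss rate is about 20% at the month-3 number and 0.00625, 29-46% under the assumed 137-103 per arm, and 5-19% over 162-103 per arm at the 5% level. For 0.63 SD it is under 5% at either level over that range.

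PFS, OS and the month-3 PRO comparisons are unaffected. This is an inexpensive improvement to a secondary PRO time point.

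**What to change.** In Section 9.6.2, for PROMIS Fatigue, FAACT and FACIT-D:

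- Add a between-arm comparison of the change from the end-of-treatment form to the 4-week form, among patients with both forms, with a 95% confidence interval. Adjust for the baseline score if wanted, but not for the end-of-treatment score.
- Report the arm A minus arm B difference at 4 weeks with its 95% confidence interval against the MIDs in Section 9.6.1. For fatigue, say in advance which end of the 3.0-5.0 point range is used; 3 points is the stricter.
- Describe symptoms as resolved only if the interval excludes a difference unfavourable to arm A as large as the MID. Otherwise report persistence as undetermined.
- State the significance level that applies to symptom tests at visits other than month 3.
- Report how many patients per arm have both forms, and note that symptoms in patients stopping for progression may reflect disease.

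The cost is SAP wording and one extra secondary or exploratory analysis per scale, on forms already scheduled. Resolution becomes harder to claim.

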#### 5.6.4 PRO Administration Instructions

All PRO questionnaires will be administered as a paper survey. Ideally, participants will complete questionnaires at the time of scheduled study visits. For the first assessment (Cycle 1), PRO should be administered prior to the administration of study drug. With the exception of the 8-item FBSI, PRO time points overlap with protocol-specified clinic visits. If the 8-item FBSI does not overlap with protocol-specified clinic visits and/or if PRO assessments are not administered in clinic, the study questionnaires will be mailed to participants who will be asked to complete questionnaires and return by mail to clinic. After 7 days, clinic or research staff may contact participants by telephone and ask participants to complete the questionnaire on paper and then read their answers over the telephone to the staff person.

In the event that the 8-item FBSI for TTD endpoint is being assessed at a protocol-specified clinic visit that includes an evaluation for progression, questionnaires will be completed before participants discuss disease status with health-care professionals. This will minimize potential bias, and is modeled after the study by Rini et al.

For the post-end of treatment PRO, we propose to administer to participants who return to clinic via paper. In the event that a participant does not return to clinic for a visit after end of treatment, we will collect the PROs via telephone. This will compensate for potential responder bias, wherein healthier patients are more likely to return to clinic and thus, to complete the post-treatment surveys. In collecting PRO data via phone, the survey will be mailed to the participant, who will complete it and then read their responses to the interviewer. This procedure will minimize mode effect, whereby participants report less symptoms burden during phone or in-person

interviews than with written surveys. This approach will approximate the completion of PROs in clinic as closely as possible.

PRO-CTCAE items will be administered on paper along with study PRO measures following procedures for PRO administration as described above. PRO-CTCAE items will be administered prior to clinic visits, or prior to participant's discussion of disease status and treatment side effects with health-care professionals. This is modeled after NCI PRO-CTCAE study procedures employed in other clinical trial validation studies. Clinicians will be instructed to complete clinician-rated treatment toxicities (CTCAE) prior to reviewing PRO-CTCAE ratings. This will minimize the extent to which PRO-CTCAE responses introduce a bias to clinician CTCAE ratings. PRO-CTCAE are currently undergoing validation and thus exploratory in nature, therefore, at this point should not be used to inform clinician CTCAE ratings. Clinicians will be instructed to review PRO-CTCAE items after clinician toxicity ratings have been completed to identify any patient-reported symptoms and toxicities that warrant clinical attention. Supportive care measures to manage treatment toxicities are described in Section [5.5](#).

#### 5.7 Duration of Therapy

Patients will receive protocol therapy unless:

- Progressive disease by RECIST criteria. See Section [6.1](#).
- Severe toxicity at discretion of treating physician or unresolved Grade 3 or 4 toxicity.
- Extraordinary Medical Circumstances: If at any time the constraints of this protocol are detrimental to the patient's health, protocol treatment should be discontinued. In this event, submit forms according to the instructions in the E2112 Forms Packet.
- Patient withdraws consent.
- Exemestane or entinostat/placebo is held for longer than permitted per Section [5.4](#).
- Patient receives non-protocol therapy, including chemotherapeutic or investigational anti-neoplastic drugs or radiation therapy to only lesion available to monitor response.

#### 5.8 Duration of Follow-up

For this protocol, all patients, including those who discontinue protocol therapy early, will be followed for response until progression even if non-protocol therapy is initiated. Upon discontinuation of treatment, patients will be followed for survival per the standard ECOG-ACRIN follow-up schedule: Every 3 months if patient is < 2 years from study entry, every 6 months if patient is 2-5 years from study entry, and every 12 months if patient is > 5 years from study entry for up to 10 years, including patients removed from study for unacceptable adverse events.

## 6. Measurement of Effect

### 6.1 Antitumor Effect – Solid Tumors

For the purposes of this study, patients should be evaluated for response according to the schedule in Section 7.

Response and progression will be evaluated in this study using the international criteria proposed by the revised Response Evaluation Criteria in Solid Tumors (RECIST) guideline (version 1.1). Changes in the largest diameter (unidimensional measurement) of the tumor lesions and the shortest diameter in the case of malignant lymph nodes are used in RECIST 1.1.

For purposes of comparability to the phase 3 study of exemestane in advanced breast cancer patients by Chia et al, enrollment in this study will attempt to achieve a target patient population that consists of approximately 80% of patients having measurable disease (with at least 1 measurable lesion at study entry) and approximately 20% of patients having non-measurable disease only.

The following general principles must be followed:

1. To assess objective response, it is necessary to estimate the overall tumor burden at baseline to which subsequent measurements will be compared. All baseline evaluations should be performed as closely as possible to the beginning of treatment and **never more than four weeks** before randomization.
2. Measurable disease is defined by the presence of at least one measurable lesion.
3. All measurements should be recorded in metric notation by use of a ruler or calipers.
4. The same method of assessment and the same technique must be used to characterize each identified lesion at baseline and during follow-up.

#### 6.1.1 Definitions

##### Evaluable for Objective Response

Only those patients who have measurable disease present at baseline, have received at least one cycle of therapy, and have had their disease re-evaluated will be considered evaluable for response. These patients will have their response classified according to the definitions stated below.

**NOTE:** Patients who exhibit objective disease progression prior to the end of cycle 1 will also be considered evaluable.

